7.4. Randomization and Blinding of Study Drug

This study will be a randomized, unblinded study involving extended release tacrolimus called Envarsus XR once a day and immediate acting tacrolimus twice a day.

8. Study Procedures

8.1. Laboratory Tests

Patients will have similar labs in both groups and will be drawn as part of the standard of care. Labs will be obtained on a daily basis while they are inpatient and on the day of clinic visit or before dialysis when they are outpatient. Commonly obtained labs include, CBC, BMP, magnesium, phosphorus level, tacrolimus level, serum calcium, urinalysis and protein/creatinine ratio. Imaging including chest x-ray, ultrasound of the transplanted kidney, CT abdomen and pelvis, CT chest, head may be obtained based on the clinical judgement. All labs and imaging will be obtained at UW Hospital and Clinics, including the use of a CAP and CLIA-certified laboratory. Labs and imaging reports will be communicated to patients by the clinical care team.

Table 1. Schedule of Study Procedures

Process	Screening	Baseline (Day 1)	Follow-up (every other day or 3 times a week till recovery from DGF))	Monthly Follow-up Visits until 3 months after transplant	Final Clinic Visit
Informed Consent	X				
Eligibility Determination	X				
Obtain demographics	X				
Study Drug Administration		X	X	X	X
Dose adjustment of Envarsus XR or tacrolimus			X	X	X

Table 2. Typical Schedule of Standard of Care Procedures

Process	Screening	Baseline (Day 1)	Follow-up (every other day or 3 times a week till recovery from DGF))	Monthly Follow-up Visits until 3 months after transplant	Final Clinic Visit
Results of Clinical Laboratory Tests	X	X	X	X	X
Medical History	X	X	X	X	X
Physical examination		X	X	X	X
Vital Sign Measurement (Temperature, Pulse, Respirations, Blood Pressure)		X	X	X	X
IR Tacrolimus Administration		X	X	X	X
Dose adjustment of IR tacrolimus			X	X	X
Decision for dialysis		X	X	X	X

8.2. Study Visits

8.2.1. Screening/Baseline

At screening/baseline visit transplant nephrology provider will decide about the need of dialysis or not and based on that information will document patient to have DGF or not. In that visit, we will review the patient's medical records. Patient will also be informed about the study and their interest will be gauged. If they are interested, then research coordinator will be informed about the potential subject.

Table 2. Medical chart review of standard of care visits

Visit*	Window	Data collection from medical record and Transplant Database
Day 1 contact	+/- 1 days	H&P, brief updates about research project
Day 3	+/- 0 days	H&P, decision for dialysis, decision to adjust study or SOC dose
Day 5	+/- 0 days	H&P, decision for dialysis, decision to adjust study or SOC dose
Day 7	+/- 0 days	H&P, decision for dialysis, decision to adjust study or SOC dose
Additional visits every 2-3 days until DGF recovery	+/- 0 days	H&P, decision for dialysis, decision to adjust study or SOC dose
Monthly up through Month 3 post diagnosis of DGF	+/- 30 days	H&P, decision for dialysis, decision to adjust study or SOC dose

*visits could be more or less depending upon the timing of DGF recovery for maximum of 3 months post-transplant.

8.2.2. Unscheduled

Subjects may have unscheduled standard of care visits due to lab results, an acute illness of undetermined cause, for other reasons, or at the discretion of the Investigator. Data will be collected from unscheduled visits and may include any of the following information;

- Adverse Event Assessment
- Medication History
- Drug Accountability
- Physical Exam
- Vital Signs (Temperature, Pulse, Respirations, Blood Pressure)
- Lab work (CBC, LFTs, DSA, imaging, biopsy)

8.2.3. Final Standard of Care Visit

Patients will be off study once they recover from DGF as documented by the provider as discharged from the DGF clinic or no need for dialysis for more than 7 days. Patients will be given the opportunity to either continue on the study medication or switch to SOC after termination from the study. Envarsus XR will not be covered by the industry, but is covered by most of the health insurance coverage. If interested, Veloxis will provide discount coupons. The final standard of care visit will also include primary evaluation, need for dose adjustment of medication and decision for dialysis. Each subject will be asked to participate in the study for up to 3 months after transplant.

9. Study Analysis

9.1. Sample Size Determination

Goal is to analyze 100 subjects total (50 in each group), with a goal to decrease DGF duration to less than 10 days in Envarsus XR group from current mean of 13.9 +/- 7 days with tacrolimus based on the power calculation.

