Total 100 patients: Obtain informed consent. Screen potential subjects by inclusion and exclusion criteria, review labs and documentation. All patients will have received or will be receiving immediate release tacrolimus as standard of care (SOC)

Visit 1 (Diagnosis of DGF)

Perform baseline assessments.
Medical records and the Transplant Database will be reviewed for the following: Routine blood test, urine test and other radiological investigation based on the clinical judgment. Commonly used test include: CBC, Lyses, BUN, Creatinine, glucose, urinalysis, urine protein/creatinine, immunosuppressive level

Visit 2 (Diagnosis of DGF)

Randomize into Tacrolimus (SOC) or Envarsus XR (study) group

Visit 3 (Daily while inpatient
Or in clinic visit)

Medical records and the Transplant Database will be reviewed for the following: Follow up assessments of study endpoints and safety.
Evaluate for need of dialysis or not. Review routine blood test performed in the morning along with urine output in last 24 hours and examinations to assess the

Visit 4 (recovery from DGF)

Medical records and the Transplant Database will be reviewed for study endpoints and safety, Routine blood test performed, H&P documenting discharged from the DGF clinic

Visit X (Time Point)

Medical records and the Transplant Database will be reviewed for the following:
Interval between transplants to the recovery of DGF
Interval between first and last dialysis
Total number of dialysis
Total number of tacrolimus or Envarsus XR dose adjustment required

2. Key Roles

2.1. *Investigator and Study Center:*

[name], MBBS
Assistant Professor (CHS)
Department of Medicine-Nephrology
[name]
[name]
[name]
[name]
[contact]
Email: [contact]

Principal Investigator:

University of Wisconsin Hospital and Clinics
[name]
[name]

Participating sites:

UW Health-University of Wisconsin Hospital and Clinics
Clinical Laboratories
[name]
[name]

Local Laboratory Services:

[name]
[name]
School of Medicine and Public Health
[name]
Email: [contact]

**ICTR Data Monitoring
Committee Contact:**

[name]
School of Medicine and Public Health
[name]
Ph: [contact]

**ICTR Study Monitoring
Service Contact:**

Veloxis Pharmaceuticals, Inc
[name],
[name]
[contact]

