5.1.3. Primary Safety Endpoints

Primary safety endpoints include: infections, malignancies, hematological complications including leukopenia, anemia, and thrombocytopenia, cardiovascular complications and events, neuropathy, tremors, gastrointestinal symptoms, uncontrolled hypertension, serious electrolytes abnormalities and immunosuppression-related adverse effects.

6. Study Subjects – Enrollment and Withdrawal

- A total of 100 subjects (50 subjects in each arm) with the diagnosis of DGF will be enrolled over a period of 2 years.
- DGF is defined as the need for a dialysis within the first week of transplant. Once potential DGF patients are identified, the transplant nephrology team will be consulted and the transplant nephrology provider will perform initial evaluation of a patient, discussion with the patient about his/her interest in participating in the research study and inform the research coordinator.
- Subjects will participate in the study until the recovery of DGF as documented by the provider as “discharged from the DGF clinic” or no need for dialysis for more than one week (7 days).
- Subject would be followed for maximum of 3 months. If they still need dialysis beyond 3 months, will be declared as primary dysfunction and will disqualify from the study.

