- Vital Signs (Temperature, pulse, respirations, and blood pressure)
- Medication History
- Routine labs (CBC, serum pregnancy test for females of child-bearing potential, BMP, or any imaging performed recently)
- Dialysis indicated or not

6.4.2. **Recruitment and Retention Strategies**

A total of 100 patients will be recruited from and enrolled at a single center, the University of Wisconsin Hospital and Clinics. Patients will be recruited and enrolled through the UW hospital inpatient transplant service and will be followed until the recovery of DGF. Based on the demographics of the state of Wisconsin and previous transplant history, more than 80% are expected to be Caucasian, approximately 40% are expected to be female.

6.5. ***Subject Capacity***

Patient's capacity to consent will be assessed by the nephrology provider. If patient is unable to consent for the study, consent to enroll will be obtained only when they are capable of giving informed consent.

6.6. ***Informed Consent***

The PI will be responsible for ensuring that valid consent is obtained and documented for all subjects. Consent will be obtained and documented during an in-person visit.

6.6.1. **Informed Consent Document**

The Informed Consent Document will include the required elements per 45 CFR 46, as well as Good Clinical Practice (GCP) Guidelines.

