6.7.2. When and How to Withdraw Subjects

If patient is unable to tolerate the study drug Envarsus XR or SOC drug tacrolimus, the subject will be withdrawn from the study, and likely be switched to other immunosuppressive medications for example cyclosporine, or belatacept or any other immunosuppressive medications based on the clinical discretion. Subjects that are withdrawn will be asked to return for one last study visit to conduct the procedures described in the last visit in the protocol.

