9.3. Subject Population(s) for Analysis

All randomized and completed study patient data will be used for primary and secondary analysis. Primary analysis include needs for dose adjustment of the Envarsus XR or tacrolimus and secondary analysis include duration of recovery from the DGF.

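### The plan uses 100 (50 per arm) both as the number enrolled and as the number analysed, with no allowance for loss, so 50 analysed per arm is reached only with zero loss

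*Combined protocol and SAP*

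**What the plan says.** The same figure appears at different stages of the combined protocol and SAP.

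- **Analysed.** Section 9.1: "Goal is to analyze 100 subjects total (50 in each group"), linked to shortening DGF from a current mean of 13.9 +/- 7 days to less than 10 days.
- **Enrolled.** Section 6: "A total of 100 subjects (50 subjects in each arm) with the diagnosis of DGF will be enrolled over a period of 2 years". Section 6.4.2: "A total of 100 patients will be recruited from and enrolled at a single center". The study summary also gives 100 subjects, 50 in each arm.
- **Flow diagram.** Figure 1, in the step before enrolment: "Total 100 patients: Obtain informed consent. Screen potential subjects by inclusion and exclusion criteria".

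The analysis population is in section 9.3: "All randomized and completed study patient data will be used for primary and secondary analysis".

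Two losses are built in. Section 6, on subjects at the end of follow-up: "If they still need dialysis beyond 3 months, will be declared as primary dysfunction and will disqualify from the study". Section 6.7.2: "If patient is unable to tolerate the study drug Envarsus XR or SOC drug tacrolimus, the subject will be withdrawn from the study". Section 6.7.3 then limits study data collection after withdrawal, and section 11.5.1 lists further grounds on which the investigator may withdraw a subject.

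The plan gives no expected loss rate, no over-enrolment and no statement for or against replacement. It also does not state the power or the sidedness of the test.

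**The concern.** The number enrolled and the number analysed can be equal only if every enrolled subject reaches the analysis. The plan's own rules make that unlikely: it names subjects who must leave, and on its natural reading 9.3 analyses only those who complete. The size quoted in 9.1 is then the best possible case, presented as the planned one.

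Two things are at stake. First, a reader of 9.1 will take the precision of the trial to be that of 50 per arm when the analysis will probably have fewer. Second, the trial is unblinded (section 7.4) and the plan is silent on replacement. The team would therefore have to decide whether to enrol further subjects after losses have occurred, with treatment assignment known. A rule written beforehand avoids that.

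This point concerns the stated number only. Bias from leaving out non-completers is a separate matter.

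**Working it through.** **Inputs**

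- Control mean 13.9 days, spread 7 (9.1). The plan does not label the 7; it is read here as an SD.
- Target below 10 days (9.1). Using 10 gives a difference of 3.9 days, the smallest that 9.1 targets.
- Significance level 0.05 (9.2), assumed two-sided.
- Student's t-test (9.2 also allows the Wilcoxon test) and 1:1 allocation (section 7).
- Power is not stated; 80% is assumed for the reproduction.
- Loss rates are not stated; 5%, 10% and 20% are assumed.

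**Step 1: reproduce the 50 per arm**

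n per arm = 2 × (z for alpha + z for power)² × SD² / difference²

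= 2 × (1.960 + 0.842)² × 49 / 15.21 = 50.6, rounded up to 51.

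The exact t-test calculation gives 51.5, rounded up to 52. So 50 per arm matches the analysable number for about 80% power, with nothing added for loss. Other conventional choices fit less well: two-sided 85% and 90% power need 58 and 68 per arm, and one-sided 80%, 85% and 90% need 40, 47 and 56.

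**Step 2: power at 50 per arm**

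Standardised difference = 3.9 / 7 = 0.557. Normal approximation: Φ(0.557 × √(50/2) − 1.960) = Φ(0.826) = 79.6%. The t-test gives 78.8%.

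**Step 3: power after loss, with 50 per arm enrolled**

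Analysed per arm = 50 × (1 − loss).

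| Assumed loss | Analysed per arm | Power, t-test | Power, normal |
|---|---|---|---|
| 0% | 50 | 78.8% | 79.6% |
| 5% | 47.5 | 76.6% | 77.5% |
| 10% | 45 | 74.3% | 75.3% |
| 20% | 40 | 69.2% | 70.3% |

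**Step 4: how likely is zero loss?**

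If each subject is lost independently with probability p, the chance that all 100 complete is (1 − p)^100. At 2% this is 0.98^100 = 13%; at 5% it is 0.95^100 = 0.6%.

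**Step 5: scale of the gap**

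Analysing 50 per arm at 10% loss would need 50 / 0.90 = 55.6, so 56 per arm or 112 in total. This shows the size of the gap; it is not a request.

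**The case against.** The strongest reply is that this is a small matter of wording. Section 9.1 states a goal, follow-up is short (mean DGF duration is 13.9 days and participation ends at recovery), and most data come from the medical record and the Transplant Database (section 10.2.1). Loss could be small, and at 5% the cost is about 2 points of power. The target is also below 10 days: at an assumed 9.5 days (difference 4.4), t-test power is 84% with 45 per arm and 79% with 40. All of this stands, and it limits the size of the point. It does not make the enrolled and analysed numbers compatible with the plan's own exclusions.

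Several stronger readings are tempting, but the documents do not support them.

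- *Nobody will be replaced.* The plan is silent; it neither allows nor forbids replacement.
- *Fifty per arm cannot be delivered.* It can, with zero loss or with replacement, and neither is ruled out.
- *Figure 1 caps consents at 100.* The box covers consent, screening and prior tacrolimus together and can be read as the study total. The summary and section 6 tie 100 to arms, which exist only after randomisation.
- *Every withdrawal ground removes a subject.* Section 11.5.1 gives the investigator a right to withdraw. Only intolerance (6.7.2) and dialysis beyond 3 months (section 6) are stated as automatic.
- *Replacement would break the randomised comparison.* Randomising further subjects does not do this in itself.

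The wording of 9.3 could also be read less strictly than completers only. If it meant all randomised subjects, with outcomes collected, most of the gap would disappear. That is a reason to define the population.

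**Conclusion.** The point holds as an inconsistency in the stated numbers. The plan enrols 100 and expects to analyse 100, while providing for exclusions and making no allowance for them. The stated 50 analysed per arm is the zero-loss case.

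The size is modest. Against a starting t-test power of about 79%, the assumed losses of 5%, 10% and 20% cost about 2, 4 and just under 10 percentage points at the smallest targeted difference. A larger true difference would soften this.

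The result rests on reading the 7 as an SD, a two-sided 0.05 test, the completer reading of 9.3, and loss rates that are assumptions because the plan gives none. A reader might infer that 50 per arm is a miscalculation. It is not: it agrees closely with the analysable number for two-sided 0.05 and 80% power. What is missing is the step from subjects analysed back to subjects randomised.

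**What to change.** 1. State in the study summary, Figure 1, section 6, section 6.4.2 and section 9.1 that 100 (50 per arm) is the number randomised, and that screen failures do not count towards it.
2. Restate 9.1 as the number expected to be analysed under the 9.3 population, over a stated range of assumed loss, with the power at each number. State the sidedness, the target power and that the 7 is an SD, if that is what was used.
3. Define the 9.3 population. If it becomes all randomised subjects, with outcomes collected from the medical record, the gap between enrolled and analysed largely closes and item 2 becomes a short sentence.
4. State whether lost subjects are replaced. Either choice is open to the sponsor, but it should be fixed in advance.

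The cost of items 1, 2 and 4 is wording in five places, one recalculated line and one sentence on replacement. The population in item 3 would also require outcome collection to continue after withdrawal, which section 6.7.3 now limits. The downside is that the stated analysed number and power become slightly less favourable. No extra patients are requested.

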9.2. Statistical Methods

Continuous data will be compared using Student's t-test or the Wilcoxon Rank Sum test, as appropriate, while categorical data will be analyzed using Fisher's exact test or chi-square test. P values < 0.05 will be considered statistically significant. Kaplan-Meier analyses will be performed to study graft survival if appropriate.

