5.1.1. Primary Study Endpoints

The primary endpoint of the study will be the interval between first dialysis and last dialysis after kidney transplant (duration of DGF).

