5.1.2. Secondary Study Endpoints

The secondary endpoint will be number of tacrolimus or Envarsus XR dose adjustments required during the period of DGF.

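### Section 9.2 does not tie the 5% level to one efficacy endpoint, and 9.3 reverses the primary and secondary roles, so the chance of a false efficacy claim is 7.0% to 9.75% rather than 5%

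*Combined protocol and SAP*

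**What the plan says.** **Endpoints.** Section 5.1.1: "The primary endpoint of the study will be the interval between first dialysis and last dialysis after kidney transplant (duration of DGF". Section 5.1.2: "The secondary endpoint will be number of tacrolimus or Envarsus XR dose adjustments required during the period of DGF". The objectives in section 4 follow the same ranking, with early recovery first and steadier tacrolimus levels second.

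**Sample size.** Section 9.1 plans 50 patients per arm, to bring DGF duration from a mean of 13.9 +/- 7 days to under 10 days. Dose adjustments play no part in it.

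**Tests.** Section 9.2 chooses tests by type of data: "Continuous data will be compared using Student's t-test or the Wilcoxon Rank Sum test, as appropriate", with Fisher's exact or chi-square for categorical data. It then states: "P values < 0.05 will be considered statistically significant". It mentions no endpoint, sidedness, order of testing or division of the 5%.

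**Analysis roles.** Section 9.3: "Primary analysis include needs for dose adjustment of the Envarsus XR or tacrolimus and secondary analysis include duration of recovery from the DGF". This is the opposite of section 5.

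**Safety.** Section 5.1.3 begins: "Primary safety endpoints include: infections, malignancies, hematological complications including leukopenia, anemia, and thrombocytopenia", and continues with further categories. Sections 11.4.4 and 11.6 describe safety data as reviewed and summarised by number and seriousness.

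**The concern.** A 5% error rate means something only when it belongs to an identified claim. Here the analysis section does not say which claim that is. Read with section 5, a significant result means a shorter DGF duration. Read with 9.3, it means fewer dose adjustments. Nothing makes a claim on one endpoint depend on the result for the other.

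If DGF duration shows no difference and dose adjustments give p = 0.03, a report could cite 9.3 and call that the primary analysis. A reader holding section 5 would call it an isolated secondary result. Both would be following the plan.

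Dose adjustments also need protection more than DGF duration does. The trial is unblinded (7.4), and the study team makes all dose changes in both arms (7.1), so the count depends partly on decisions by people who know the allocation.

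**Working it through.** **1. Which test was the 5% meant for?** Reproduce the sample size in 9.1.

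- Inputs from 9.1: difference 13.9 − 10 = 3.9 days; 7 read as the standard deviation; 50 per arm.
- Assumed, because not stated: two-sided 0.05 and 80% power.
- Formula: n per arm = 2 × (1.960 + 0.842)² × 7² / 3.9² = 50.6, rounded up to 51, against the planned 50.
- Power at 50 per arm: the standard error is 7 × √(2/50) = 1.4 and 3.9/1.4 = 2.786, so power is Φ(2.786 − 1.960) = 79.6% (78.8% with the t distribution).
- Other settings do not fit: one-sided at 80% power needs 40 per arm, two-sided at 85% needs 58, and two-sided at 90% needs 68.

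The planned number matches a single two-sided 5% test of DGF duration.

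**2. What does the text allow?**

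| Place | DGF duration | Dose adjustments |
|---|---|---|
| 5.1.1 and 5.1.2 | primary | secondary |
| 9.1 | basis of the sample size | not used |
| 9.3 | secondary analysis | primary analysis |
| 9.2 | p < 0.05 | p < 0.05 |

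Two tests are each read at 0.05, and the documents disagree on which leads.

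**3. Chance of at least one false claim.** Suppose there is no true effect on either endpoint.

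- Independent test statistics: 1 − 0.95² = 9.75%.
- Correlation ρ: 1 − P(|Z₁| < 1.96 and |Z₂| < 1.96), with Z₁ and Z₂ bivariate normal.

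| ρ | 0 | 0.3 | 0.5 | 0.7 | 0.9 |
|---|---|---|---|---|---|
| At least one p < 0.05 | 9.75% | 9.5% | 9.1% | 8.3% | 7.0% |

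The documents give no correlation, so the range is shown. Some positive correlation is plausible, since dose adjustments are counted over the period of DGF and a longer period leaves more time for them.

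**4. What would each remedy do?**

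- *Fixed sequence* (DGF duration at 0.05, then dose adjustments at 0.05 only after success). If neither effect is real, a false claim requires DGF duration to be falsely significant first, so the chance is at most 5%. If only the effect on DGF duration is real, the sole possible false claim is on dose adjustments, again at most 5%. Power for DGF duration stays at 78.8% to 79.6% with 50 per arm.
- *Splitting the level* (0.025 each). The error is at most 5%, but power for DGF duration falls to Φ(2.786 − 2.241) = 70.7% (69.4% with the t distribution). About 62 per arm would be needed for 80%.

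The fixed sequence controls the same error at no cost to the primary test.

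**The case against.** The strongest reply is that the protocol does rank its endpoints. Sections 4, 5.1.1 and 5.1.2 put DGF duration first, and 9.1 sizes the trial on it alone. With one named primary and one named secondary, a reader can see when a significant secondary stands beside a failed primary. For one secondary endpoint in a small trial that section 7 says is not intended to support a new indication or a labelling change, formal gating may look like a matter of taste.

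Much of this stands. It would be wrong to say that the plan has no order of endpoints, and the excess error is modest. The reply would be close to sufficient if 9.3 agreed with section 5. It does not, and 9.3 is where an analyst looks for the primary analysis, so the labels cannot settle which endpoint carries the 5%.

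A reader might go further. Section 9.2 covers categorical data in general, and 5.1.3 calls its safety categories primary, so one might infer that each safety comparison is also a significance claim. Counting the two efficacy endpoints plus 10 safety categories (12 if the three hematological items are split) would give 1 − 0.95¹² = 46% or 1 − 0.95¹⁴ = 51%. The documents do not support that reading. They state no safety hypothesis and name no between-arm safety test, and 11.4.4 and 11.6 describe review and summary. The figures also require independent tests, although several categories overlap, and a full 5% error for each, although Fisher's test on rare events has less. What remains is that 9.2 does not exclude safety from its rule; one sentence would do so.

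**Conclusion.** The point holds for the two efficacy endpoints. Section 9.2 attaches the 5% level to no endpoint and 9.3 contradicts section 5 on which comes first. If either result may be claimed alone, the chance of a false efficacy claim is 7.0% to 9.75%, against the intended 5%. If DGF duration were fixed as the only confirmatory test, it would be 5%.

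The range assumes no true effect on either endpoint, two-sided tests, approximately normal test statistics and a correlation between 0 and 0.9. The power figures also assume that 7 days is a standard deviation. The error range does not depend on that.

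This is a contradiction to resolve and a moderate excess in error. It does not show that every comparison in the trial carries a claim. The correction is worth making because it costs almost nothing and must precede any look at results by arm to be credible.

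**What to change.** Make both changes together; changing 9.2 alone would leave it in conflict with 9.3.

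1. **Section 9.3.** State that the primary analysis is of DGF duration as defined in 5.1.1, and the secondary analysis is of the number of dose adjustments as defined in 5.1.2.
2. **Section 9.2.** Replace the sentence on significance with: *The two-sided 0.05 level applies to the primary endpoint (5.1.1). The secondary endpoint (5.1.2) is tested at two-sided 0.05 only if the primary is significant; otherwise it is reported as an estimate with a 95% confidence interval. Safety and other outcomes are reported as counts and differences with 95% confidence intervals, without a significance statement.*

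The cost is an amendment to the wording of two sections. The sample size, data collection and power for DGF duration do not change. The one loss is that a difference in dose adjustments cannot be claimed as significant if DGF duration fails; it would still be reported with its interval.
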